APPENDIX G. NEW YORK HEART ASSOCIATION FUNCTIONAL CLASSIFICATION

The table below describes the New York Heart Association Functional Classification system (adapted from Criteria Committee NY Heart Association 1994). It places patients in 1 of 4 categories based on how much they are limited during physical activity.

Class	Patient Symptoms
I	No limitation of physical activity. Ordinary physical activity does not cause undue fatigue, palpitation, dyspnea (shortness of breath).
II	Slight limitation of physical activity. Comfortable at rest. Ordinary physical activity results in fatigue, palpitation, dyspnea (shortness of breath).
III	Marked limitation of physical activity. Comfortable at rest. Less than ordinary activity causes fatigue, palpitation, or dyspnea.
IV	Unable to carry on any physical activity without discomfort. Symptoms of heart failure at rest. If any physical activity is undertaken, discomfort increases.

APPENDIX H. ACTIVITY SCHEDULE

The following tables show the required activities. The individual activities are described in detail in the **Operations Manual** ([Appendix J](#)).

Table 3. Schedule of Activities

Activity	Screening period (4 weeks)	Double Blind Treatment Period (12 weeks)				Active Treatment Extension Period (dose blinded, 12 weeks)			Follow up Period (30 days)
	Visit 1/ Screening/ Baseline	Visit 2	Visit 3	Visit 4	Visit 5/ ET DB	Visit 6	Visit 7	Visit 8/ ET EX	Visit 9/EOS
	Week 4 (Day 35 to Day 28)	Day 1	Week 4 (Day 28) ± 3 days	Week 8 (Day 56) ± 3 days	Week 12 (Day 84) + 3 days	Week 16 (Day 112) ± 3 days	Week 20 (Day 140) ± 3 days	Week 24 (Day 168) + 3 days	Week 28 (Day 198/ 30 days after the last dose of study drug) + 3 days
INTERVIEWS & QUESTIONNAIRES									
Informed consent	✓								
Informed consent for biomarker research (optional)	✓								
Eligibility criteria	✓	✓							
Demographics	✓								
Medical history	✓								
Migraine headache history	✓								
Review prior medications including all migraine prophylactic medication use	✓								
Menstrual cycle assessment	✓	✓	✓	✓	✓	✓	✓	✓	✓
Adverse events	✓	✓	✓	✓	✓	✓	✓	✓	✓
Concomitant medications/concurrent procedures	✓	✓	✓	✓	✓	✓	✓	✓	✓
Provide eDiary, instructions and training	✓								
eDiary data collection	✓	✓	✓	✓	✓				
Collect eDiary device		✓			✓				
Review of eDiary data and compliance		✓	✓	✓	✓				

Activity	Screening period (4 weeks)	Double Blind Treatment Period (12 weeks)				Active Treatment Extension Period (dose blinded, 12 weeks)			Follow up Period (30 days)
	Visit 1/ Screening/ Baseline	Visit 2	Visit 3	Visit 4	Visit 5/ ET DB	Visit 6	Visit 7	Visit 8/ ET EX	Visit 9/EOS
	Week 4 (Day 35 to Day 28)	Day 1	Week 4 (Day 28) ± 3 days	Week 8 (Day 56) ± 3 days	Week 12 (Day 84) + 3 days	Week 16 (Day 112) ± 3 days	Week 20 (Day 140) ± 3 days	Week 24 (Day 168) + 3 days	Week 28 (Day 198/ 30 days after the last dose of study drug) + 3 days
C SSRS (eTablet)	✓	✓	✓	✓	✓	✓	✓	✓	✓
ASC 12 (eTablet)	✓								
HIT 6 (eTablet)		✓	✓	✓	✓				
PGIC (eTablet)					✓				
PGI S (eTablet)		✓	✓	✓	✓				
WPAI:MIGRAINE (eTablet)		✓	✓	✓	✓				
PSSM (eTablet)			✓	✓	✓				
EQ 5D 5L (eDiary)	✓	✓	✓	✓	✓				
MIDAS (eTablet)		✓			✓				
MSQ v2.1 (eTablet)		✓	✓	✓	✓				
PROMIS PI (eTablet)		✓	✓	✓	✓				
PHQ 9 (eTablet)		✓			✓				
 LOCAL LABS & EXAMS									
Physical examination	✓				✓			✓	✓
Height (Visit 1 only) and weight	✓	✓	✓	✓	✓	✓	✓	✓	✓
Vital sign measurements	✓	✓	✓	✓	✓	✓	✓	✓	✓
12 lead ECG	✓				✓			✓	

Activity	Screening period (4 weeks)	Double Blind Treatment Period (12 weeks)				Active Treatment Extension Period (dose blinded, 12 weeks)			Follow up Period (30 days)
	Visit 1/ Screening/ Baseline	Visit 2	Visit 3	Visit 4	Visit 5/ ET DB	Visit 6	Visit 7	Visit 8/ ET EX	Visit 9/EOS
	Week 4 (Day 35 to Day 28)	Day 1	Week 4 (Day 28) ± 3 days	Week 8 (Day 56) ± 3 days	Week 12 (Day 84) + 3 days	Week 16 (Day 112) ± 3 days	Week 20 (Day 140) ± 3 days	Week 24 (Day 168) + 3 days	Week 28 (Day 198/ 30 days after the last dose of study drug) + 3 days
Urine pregnancy test		✓	✓	✓	✓	✓	✓	✓	✓
 CENTRAL LABS									
Serum pregnancy test	✓								
Clinical laboratory test	✓	✓	✓	✓	✓	✓	✓	✓	✓
Urine drug screen	✓								
PK plasma sample		✓	✓	✓	✓				
Optional biomarker sample: whole blood DNA		✓							
Optional biomarker sample: saliva and plasma		✓			✓			✓	
 TREATMENT									
Access IRT	✓	✓	✓	✓	✓	✓	✓	✓	
Randomization		✓							
Dispense study drug		✓	✓	✓	✓	✓	✓		
Review of study drug compliance and accountability			✓	✓	✓	✓	✓	✓	

Table 4. Schedule of Activities for Remote Visits (only after completion of Visit 3)

Activity	Double blind Treatment Period (12 weeks)		Active Treatment Extension Period (dose blinded, 12 weeks)			Follow up Period (30 days)
	Visit 4	Visit 5	Visit 6	Visit 7	Visit 8/ ET EX	Visit 9/ EOS
	Week 8 (Day 56) ± 3 days	Week 12 (Day 84) + 3 days	Week 16 (Day 112) ± 3 days	Week 20 (Day 140) ± 3 days	Week 24 (Day 168) + 3 days	Week 28 (Day 198/30 days after the last dose of study drug) + 3 days
INTERVIEWS & QUESTIONNAIRES						
Adverse events	✓	✓	✓	✓	✓	✓
Concomitant medications/concurrent procedures	✓	✓	✓	✓	✓	✓
eDiary data collection	✓	✓				
Review of eDiary data and compliance	✓	✓				
C SSRS (eTablet)	✓	✓	✓	✓	✓	✓
HIT 6 (eTablet)	✓	✓				
PGIC (eTablet)		✓				
PGI S (eTablet)	✓	✓				
WPAI:MIGRAINE (eTablet)	✓	✓				
PSSM (eTablet)	✓	✓				
EQ 5D 5L (eDiary)	✓	✓				
MIDAS (eTablet)		✓				
MSQ v2.1 (eTablet)	✓	✓				
PROMIS PI (eTablet)	✓	✓				
PHQ 9 (eTablet)		✓				

Activity	Double blind Treatment Period (12 weeks)		Active Treatment Extension Period (dose blinded, 12 weeks)			Follow up Period (30 days)
	Visit 4	Visit 5	Visit 6	Visit 7	Visit 8/ ET EX	Visit 9/ EOS
	Week 8 (Day 56) ± 3 days	Week 12 (Day 84) + 3 days	Week 16 (Day 112) ± 3 days	Week 20 (Day 140) ± 3 days	Week 24 (Day 168) + 3 days	Week 28 (Day 198/30 days after the last dose of study drug) + 3 days
 LOCAL LABS & EXAMS						
Urine pregnancy test	✓	✓	✓	✓	✓	✓
 TREATMENT						
Dispense study drug	✓	✓	✓	✓		
Review of study drug compliance and accountability	✓	✓	✓	✓	✓	

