2.2 Benefits and Risks to Subjects

Based on currently available data, atogepant has demonstrated efficacy in significantly reducing the number of migraine and headache days at doses of 10, 30, and 60 mg QD in episodic migraine and 60 mg QD in chronic migraine; and has been safe and well tolerated. The most common adverse drug reactions in clinical trials are nausea, constipation, fatigue/somnolence, decreased appetite, and decreased body weight.

Asymptomatic AST and ALT elevations above $3 \times$ the ULN were rarely observed during the clinical trials in adults and there was a balance in the incidence of these elevations between atogepant treatment arms and placebo. No cases of severe liver injury or concurrent bilirubin elevations ($\geq 2 \times$ ULN) were observed during the clinical trials in adults. Hepatotoxicity events are under close surveillance and monitoring during this study. An external hepatic event adjudication committee should provide blinded surveillance, monitoring, and adjudication of events of post-treatment elevations of ALT and/or AST $\geq 3 \times$ ULN in this study. In addition, an independent DSMB should review safety data throughout the study and make recommendations to the sponsor including modification or early termination of the study.

A newly identified risk of hypersensitivity, including anaphylaxis, dyspnea, rash, pruritus, urticaria, and facial edema, with the use of atogepant has been identified based on postmarketing safety reports. Serious hypersensitivity reactions, such as anaphylaxis, are rare, idiosyncratic in nature, and treatable with well-established treatment options as part of the standard of care.

As such, considering atogepant's established efficacy and safety profile and the measures planned to minimize risk to subjects participating in this study, the benefits of treatment with atogepant outweigh the risks, including serious hypersensitivity reactions, such as anaphylaxis.

The protocol is designed to ensure that safety is assessed adequately throughout the study. Although this is a 12-week placebo-controlled trial with a 12-week active treatment extension (with atogepant dose blinded), if a study subject experiences a migraine attack during the study, the subject is allowed to treat the migraine with their acute migraine treatment. Overall, the assessment of benefit/risk of atogepant is favorable.

For further details regarding atogepant, please refer to the current atogepant Investigator's Brochure.

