3.5 Safety Endpoints

Safety evaluations include AE monitoring, vital sign measurements, ECG variables, clinical laboratory testing (hematology, chemistry, and urinalysis), and C-SSRS as measures of safety and tolerability for the entire study duration.

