5.5 Withdrawal of Subjects and Discontinuation of Study

Early Discontinuation of Subjects

A premature discontinuation will occur when a subject who signed the ICF and has been randomized ceases participation in the study, regardless of circumstances, before completion of the study. A subject may voluntarily withdraw or be withdrawn from the study at any time for reasons including, but not limited to, the following:

- Clinically significant abnormal laboratory results or AEs, which rule out continuation of the study drug, as determined by the investigator or the sponsor.
- The investigator believes it is in the best interest of the subject.
- The subject requests withdrawal from the study.
- Eligibility criteria violation was noted after the subject started study drug and continuation of the study drug would place the subject at risk.
- Introduction of prohibited medications or dosages and continuation of the study drug would place the subject at risk.
- The subject becomes pregnant while on study drug.
- Subject is significantly noncompliant with study procedures, which would put the subject at risk for continued participation in the trial.

ALT or AST Elevations

Study drug must be interrupted if any of the following criteria are met:

- ALT or AST $\geq 3 \times$ ULN and the subject is symptomatic with the appearance of fatigue, nausea, vomiting, right upper quadrant pain or tenderness, fever, rash, or eosinophilia ($> 5\%$)
- ALT or AST $\geq 3 \times$ ULN and total bilirubin $> 2 \times$ ULN
- ALT or AST $\geq 3 \times$ ULN and INR > 1.5
- ALT or AST $\geq 5 \times$ ULN for more than 2 weeks
- ALT or AST $\geq 8 \times$ ULN

The subject may be rechallenged with study drug only after careful evaluation of the case including thorough evaluation of potential alternative etiologies and approval of the sponsor TA MD. For subjects who are not rechallenged with study drug, they should be discontinued from the study and complete an ET visit and Follow-up visit (30 days after the last dose of study drug). Subjects should receive appropriate follow-up as per standard of care.

Withdrawal Criteria

Subjects may voluntarily withdraw from the study at any time.

The subjects must withdraw from the study at any time for:

- Female subjects who become pregnant (Section 6.1).

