- Subjects who meet study drug discontinuation criteria related to abnormal liver function tests (Section 6.1) and advised not to be rechallenged will be withdrawn from the study and should refrain from taking study drug. The subject should return to the clinic for the ET visit and the Follow-up visit.
- Subjects who reply with "yes" to Type 4 or 5 in the suicidal ideation section or "yes" to any question in the suicidal behavior section of the C-SSRS at Visits 3 through 8 must be withdrawn from the study and should receive appropriate follow-up as in routine clinical practice, including the ET and the Follow-up visits.
- Subjects who experience any serious AE of hypersensitivity or anaphylactic reaction.
- Subjects who experience a nonserious AE of hypersensitivity unless there is clear alternative etiology.
- Subjects with a condition and/or a situation that, in the investigator's opinion, may put the subject at significant risk, may confound the study results, or may interfere significantly with the subject's participation in the study must be withdrawn from treatment.

For subjects to be considered lost to follow-up, reasonable attempts must be made to obtain information on the subject's final status. At a minimum, 2 telephone calls must be made and 1 certified letter must be sent and documented in the subject's source documentation.

Study Termination

AbbVie may terminate this study prematurely, either in its entirety or at any site. The investigator may also stop the study at their site if they have safety concerns. If AbbVie terminates the study for safety reasons, AbbVie will promptly notify the investigator.

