10.3 Analysis of Laboratory Data

The clinical laboratory tests defined in the protocol operations manual (e.g., hematology, clinical chemistry, and urinalysis) will be summarized.

Each laboratory variable will be summarized by treatment group for all time points (starting with Baseline) with the number of non-missing observations, mean and standard deviation, median, Q1, Q3, minimum and maximum. Mean change from baseline to each applicable post-baseline visit will be summarized for selected laboratory variables, with the number of observations, baseline mean, and visit mean. In addition, descriptive statistics for values and changes from the baseline values in conventional units at each assessment time point will be presented for selected clinical laboratory parameters listed in [Appendix D](#). A description of reporting the lab values in conventional units in patient narratives (along with the standard reporting in SI units) is presented at the end of [Appendix D](#).

Laboratory abnormalities will be evaluated based on Potentially Clinically Significant (PCS) criteria ([Appendix C](#), Table C-1). For each laboratory PCS criterion, the number

and percentage of subjects who have a laboratory value meeting the criteria will be summarized by treatment group. Listings will be provided to summarize subject-level laboratory data for subjects meeting PCS criteria.

The number and percentage of subjects meeting each of the criteria for postbaseline hepatic laboratory abnormalities listed in [Appendix C](#), Table C-2 will be summarized. The percentages will be calculated relative to the number of subjects with at least 1 available postbaseline assessment. The numerator will be the total number of subjects having at least 1 postbaseline value that meets the specific category during the study. A supportive listing will also be provided.

The number and percentage of subjects with an adjudicated case (i.e., $ALT \geq 3 \times ULN$ and/or $AST \geq 3 \times ULN$) will be summarized by treatment group and by relationship of ALT or AST elevation to study medication. The percentages will be calculated relative to the number of subjects with at least 1 adjudicated case. The numerator will be the number of subjects with at least 1 adjudicated case in the specific category of relationship. If a subject has more than 1 adjudicated case, he or she will be counted in the most relevant category of relationship.

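### No remote visit is scheduled to yield the ALT/AST values that the hepatic interruption criteria need, and the SAP can count a subject with no later liver test as a non-event

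*Protocol*

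**What the plan says.** Protocol Appendix H gives two schedules and presents both as required activities. Table 3 ticks "Clinical laboratory test", "Vital sign measurements" and weight at all nine visits, the 12-lead ECG at Visits 1, 5 and 8, and the physical examination at Visits 1, 5, 8 and 9. The other schedule, "Table 4. Schedule of Activities for Remote Visits (only after completion of Visit 3", covers Visits 4 to 9, including the extension early-termination visit and the end-of-study visit. Its only laboratory or examination row is a urine pregnancy test. It has no central-laboratory block, and it ticks drug dispensing at Visits 4 to 7.

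Other sections commit the trial to measurement:

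- Section 2.2: "Hepatotoxicity events are under close surveillance and monitoring during this study".
- Section 3.5 names laboratory tests, vital signs and ECG "as measures of safety and tolerability for the entire study duration".
- Section 5.5: "Study drug must be interrupted if any of the following criteria are met", followed by five criteria.
- Section 6.1 asks investigators to watch routinely for laboratory signs of AEs for the length of the study.

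For hepatic abnormalities, SAP 10.3 says: "The percentages will be calculated relative to the number of subjects with at least 1 available postbaseline assessment". It counts events over the whole study. SAP 10.1 says safety summaries are given separately for each treatment period.

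**The concern.** Table 4 and the safety sections cannot all be followed as written. A subject seen remotely still receives drug, but that visit is not scheduled to produce the values on which Section 5.5 and two of the three adverse events of special interest rest. Remote AE interviews are a weak substitute: Section 2.2 describes the transaminase elevations seen in earlier trials as asymptomatic, and four of the five criteria in Section 5.5 name no symptom.

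The analysis repeats the gap. SAP 10.2.5 reports the hepatic events of special interest only through the laboratory section, and the SAP version history explains that these data are not collected on the AE form. An elevation that is not measured therefore does not appear as a hepatic event of special interest, while the subject may still be counted in the denominator. The DSMB's laboratory, ECG and vital-sign reviews depend on the same data.

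**Working it through.** **1. Row-by-row comparison of Tables 3 and 4.** Post-dose visits are Visits 3 to 9.

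| Assessment | Post-dose, Table 3 | Of these, at Visits 4-9 | Table 4 | Left if Visits 4-9 are all remote |
|---|---|---|---|---|
| Clinical laboratory test | 7 | 6 | 0 | 1 |
| Vital signs | 7 | 6 | 0 | 1 |
| Weight | 7 | 6 | 0 | 1 |
| ECG | 2 | 2 | 0 | 0 |
| Physical examination | 3 | 3 | 0 | 0 |

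**2. What the criteria need.** The five criteria in Section 5.5 are ALT or AST:

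- at least 3 x ULN with symptoms;
- at least 3 x ULN with raised bilirubin;
- at least 3 x ULN with raised INR;
- at least 5 x ULN for more than two weeks;
- at least 8 x ULN.

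Each needs a measured transaminase, and the fourth needs repeated values. Table 4 schedules none.

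**3. Length of the gap (nominal days from Table 3).** With every visit from Visit 4 on remote, the last scheduled liver test is on Day 28 and treatment ends on Day 168:

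168 - 28 = 140 days; 140/168 = 83%.

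A placebo subject who switches after Day 84 spends 168 - 84 = 84 days on atogepant. If Visits 6, 7 and 8 are all remote, no liver test is scheduled on any of them. If Visit 5 is remote too, the last value before the first atogepant dose is the Week 4 value, 8 weeks earlier. When only some visits are remote, the loss is confined to those visits.

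**4. How many switched subjects could be affected.** Protocol Table 2 has 130 randomized and 123 effective subjects per arm: 130 x (1 - 0.054) = 123. Re-randomization is 1:1:1, so 123/3 = 41 to 130/3 = 43 subjects per dose at most. The share using remote visits is not given. Assuming 5% to 20% for illustration, 0.05 x 123 = 6 to 0.20 x 123 = 25 switched subjects across the three doses.

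**5. Effect on the SAP percentage.** Safety baseline is the last value before first dose, so a Week 4 value is postbaseline. For a switched subject it was taken on placebo. The wording of SAP 10.3 lets that value alone keep the subject in the denominator. Let p be the true proportion with an elevation in the extension and f the share with no in-period test, with equal risk in both groups (an assumption). Then:

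- all subjects kept in the denominator: expected percentage = p(1 - f);
- only subjects with an in-period value: expected percentage = p.

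With f assumed at 5% to 20%, the first form reports 95% to 80% of the true rate.

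**The case against.** A reader might infer that hepatic interruption cannot be triggered at all for a subject seen remotely. The documents do not support that. The Section 5.5 criteria are not tied to scheduled visits, AEs are still collected at each remote visit, Section 6.1 keeps the monitoring duty in force, and nothing bars an unscheduled test. Nor do they support a complete gap after Week 4 for every remote subject: no visit is required to be remote.

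Two further points concern Table 4 itself. Appendix H refers to the Operations Manual for detail, and the manual may limit remote visits or provide for make-up tests. Table 4 is also not exhaustive: it has no row for IRT access, although Section 5.7 assigns kits through the IRT and the table ticks dispensing. Both points stand, and they limit the size of the finding. They do not reconcile two schedules that are each presented as required and that differ on exactly these tests.

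It is also tempting to see a contradiction in the rule for subjects withdrawn for liver tests, "The subject should return to the clinic for the ET visit and the Follow-up visit". That can be read as a specific rule alongside a general remote option, since Table 4 does not say such subjects may use it.

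On the analysis, SAP 10.1 already splits summaries by period, and SAP 10.3 and 10.4 report the number of non-missing values at each time point, so missing extension data would be visible there. A subject with no postbaseline ECG also drops out of the SAP 10.5.1 denominator for potentially clinically significant values, so the claim that ECG results would look clean for such a subject fails. What remains is that SAP 10.3 does not require an in-period value and counts events over the whole study. In 10.5.1, an ECG at Visit 5 can keep a subject with a remote Visit 8 in an extension percentage.

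**Conclusion.** The point holds as a conflict within the protocol and an ambiguity in the SAP. On the pages supplied, no remote visit is scheduled to produce the ALT/AST values on which Section 5.5 and the hepatic events of special interest depend, and this disagrees with Sections 2.2, 3.5, 5.5 and 6.1.

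The 140-day and 84-day figures are upper bounds. The first needs every visit from Visit 4 on to be remote, the second needs Visits 6 to 8 to be remote, and both assume that the Operations Manual does not restore testing. The real extent depends on uptake, which the documents do not state.

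The SAP wording needs tightening whatever the manual says, because a period percentage should rest on values from that period. The bias runs towards too few hepatic events. Under equal risk, its relative size equals the share of counted subjects with no in-period test.

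**What to change.** **Protocol.** Reconcile Table 4 with Table 3 and Sections 2.2, 3.5, 5.5 and 6.1, so that the documents agree on whether these assessments are done when a dispensing, early-termination or Follow-up visit is remote. Which way to resolve it is the sponsor's clinical decision, and no rule is proposed here. If the Operations Manual already settles it, a footnote to Table 4 would be enough.

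**SAP 10.3.** Make the hepatic numerator and denominator period-specific: a subject counts in a period only with at least one ALT or AST taken in that period, and only elevations in that period count as its events.

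**SAP 10.5.1.** Apply the same rule to extension ECG percentages.

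**Both SAP sections.** Report by arm and period the number of dosed subjects with no in-period value.

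**Cost.** A clarification of one schedule table and a few SAP sentences. Denominators become slightly smaller.

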APPENDIX I. PROTOCOL SUMMARY OF CHANGES

Previous Protocol Versions

Protocol	Date
Version 1.0	27 Mar 2020
Version 2.0 (Amendment #1)	11 Jan 2022
Version 3.0 (Amendment #2)	29 Apr 2022
Administrative Change 1	02 Jun 2022
Version 4.0 (Amendment #3)	08 Dec 2022
Version 5.0 (Amendment #4)	20 Feb 2023
Version 6.0 (Amendment # 5)	30 Oct 2023

The purpose of this version is to update the protocol to add information on a newly identified risk of hypersensitivity and anaphylactic reactions with the use of atogepant. Additionally, some minor editorial changes were made during this amendment:

- Section 2.2 Added description of hypersensitivity reactions and anaphylaxis to the discussion of benefits and risks to subjects.
- Section 5.3 Updated with strong OATP1B1 and OATP1B3 inhibitors to align with the clarification letters.
- Section 5.5 Added withdrawal criteria for nonserious hypersensitivity and serious hypersensitivity or anaphylactic reactions.
- Appendix C Updated signatories based on new SOP.
- Appendix E
 - Updated with strong OATP1B1 and OATP1B3 inhibitors to align with the clarification letters.
 - Updated with strong/moderate CYP3A4 inducers for diabetes and glucocorticoids.
